**Table 9.4.1-1: Clinical Laboratory Assessments**

Serology (at screening)
Serum for hepatitis C antibody (if Hepatitis C antibody is positive reflex to hepatitis C RNA) or hepatitis C RNA, hepatitis B surface antigen, HIV-1 and HIV-2 antibodies. (Testing for HIV-1 and HIV-2 must be performed at sites where mandated by local requirements [Appendix 11])
C-reactive protein
Other Analyses
Pregnancy test (women of child-bearing potential [WOCBP] only: minimum sensitivity 25 IU/L or equivalent units of human chorionic gonadotropin [HCG]), Section 2).
Follicle stimulating hormone (FSH) screening -only required to confirm menopause in women < age 55 (if needed to document postmenopausal status as defined in Appendix 4)

## 9.4.2 Imaging Safety Assessment

Not applicable.

## 9.5 Pharmacokinetics

### 9.5.1 Background

#### **Pharmacokinetics of BMS-986205**

Preliminary PK data are available from participants who received BMS-986205 in Study CA017003 at doses of 25 to 400 mg during monotherapy. Following BMS-986205 administration with a light meal, the median Tmax was 3 to 4 hours (ranging from 1 to 8 hours). Geometric mean apparent clearance (CL/F) values on Day 14 ranged from 12.5 to 20.8 L/h. Accumulation based on AUC(0-24h) between Days 1 and 14 ranged from 2.1- to 3.6-fold, supportive of once daily dosing of BMS-986205. Based on the observed accumulation index of AUC, an effective half-life in the range of 26 hours to 51 hours can be estimated. Following a single dose administration of 100 mg BMS-986205, the mean terminal half-life of BMS-986205 was determined to be 98 hours. Full details on the clinical pharmacology aspects of BMS-986205 can be found in the BMS-986205 IB.

#### **Pharmacokinetics of Nivolumab**

The PK of nivolumab were studied in participants over a dose range of 0.1 to 10 mg/kg administered as a single dose or as multiple doses of nivolumab every 2 or 3 weeks. The geometric mean (% CV%) CL was 9.5 mL/h (49.7%), geometric mean volume of distribution at steady state (Vss) was 8.0 L (30.4%), and geometric mean elimination half-life was 26.7 days (101%). Steady-state concentrations of nivolumab were reached by 12 weeks when administered at 3 mg/kg Q2W, and systemic accumulation was approximately 3 fold. The exposure to nivolumab increased dose proportionally over the dose range of 0.1 to 10 mg/kg administered every 2 weeks. The clearance of nivolumab increased with increasing body weight. The PPK analysis suggested that the following factors had no clinically important effect on the CL of nivolumab: age (29 to 87 years), gender, race, baseline LDH, PD-L1. A PPK analysis suggested no difference in CL of nivolumab based on age, gender, race, tumor type, baseline tumor size, and hepatic impairment.

Although ECOG status, baseline glomerular filtration rate (GFR), albumin and body weight had an effect on nivolumab CL, the effect was not clinically meaningful.

Full details on the clinical pharmacology aspects of nivolumab can be found in the nivolumab IB.

### 9.5.2 Immunogenicity Assessments

Per Protocol Amendment 04, ONLY immunogenicity assessments will be collected. Samples for anti-drug antibody (ADA) assessments will be collected from all participants receiving study treatment. Immunogenicity samples will be analyzed for anti-nivolumab antibody. Given that BMS-986205 is a small molecule, the immunogenicity of BMS-986205 will not be evaluated.

Table 9.5.2-1 lists a detailed sampling schedule to be followed for the assessment of immunogenicity for all study treatments, where applicable. Treatment assignments will be released to the bioanalytical laboratory in order to minimize unnecessary analysis of samples. All on-treatment immunogenicity sample collections are intended to align with days on which nivolumab and BMS-986205 are co-administered. If it is known that a dose is going to be delayed, then the predose sample should be collected just prior to the delayed dose. However, if a predose sample is collected but the dose is subsequently delayed, an additional predose sample should not be collected.

Separate detailed instructions for the collection, processing, handling, labeling, storage, and shipment of immunogenicity samples will be provided in the laboratory procedures manual.

**Table 9.5.2-1: Anti-drug Antibody Sampling Schedule for Nivolumab**

Study Day of Sample Collection (1 cycle = 4 weeks)	Event	Time Relative to Dosing a Hour:Minutes	ADA Blood Sample b  Nivolumab (Serum)
Cycle 1, Day 1	Predose c	00:00	X
Cycle 3, Day 1	Predose c	00:00	X
Cycle 6, Day 1	Predose c	00:00	X
Cycle 10, Day 1	Predose c	00:00	X
First 2 Follow-up Visits d	FU1		X
	FU2		X

Abbreviations: FU = follow-up; ADA=anti-drug antibody

a For nivolumab samples, the time of collection is relative to the start of nivolumab infusion.

b ADA samples will be collected for nivolumab only. No ADA sample collection is required for BMS-986205.

c Predose samples should be collected just prior to administration of nivolumab (preferably within 30 minutes). If it is known that a dose is going to be delayed, then the predose sample should be collected just prior to the delayed dose. However, if a predose sample is collected but the dose is subsequently delayed, an additional predose sample should not be collected.

d If a participant permanently discontinues study drug treatment during the sampling period, then they will move to sampling at follow-up visits.

## **9.6 Pharmacodynamics**

[figure not shown]
Per Protocol Amendment 04, pharmacodynamics will not be collected.

[figure not shown]
## **9.7 Pharmacogenomics**

See [Section 9.8](#).

## **9.8 Biomarkers**

Per Protocol Amendment 04, biomarkers will not be collected.

## 9.9 Health Economics OR Medical Resource Utilization and Health Economics

Per Protocol Amendment 04, health economics/medical resource utilization and health economics parameters will not be evaluated.

## 9.10 Immunogenicity Assessments

See [Table 9.5.2-1](#) for timing of blood sampling for immunogenicity assessments.

Nivolumab immunogenicity will be reported for ADA positive status (such as persistent positive, other positive, only last sample positive, or baseline positive) and ADA negative status, relative to baseline. In addition, presence of neutralizing antibody may be reported, if applicable. The effect of immunogenicity on safety may be explored.

## 9.11 Other Assessments

### 9.11.1 Patient-reported Outcomes

Per Protocol Amendment 04, patient-reported outcomes will not be evaluated.

## 10 STATISTICAL CONSIDERATIONS

Per Protocol Amendment 04, only safety and immunogenicity analyses will be conducted.

### 10.1 Sample Size Determination

Per Protocol Amendment 04, sample size will be limited to the participants enrolled as of 02-Jun-2021. The following sample size considerations refer to the original study design.

The sample size of this study is calculated in order to estimate the CR rate in treated participants with CIS randomized to receive either nivolumab monotherapy, nivolumab combined with intravesical BCG, or nivolumab combined with BMS-986205.

Using modified randomization based on BCG availability and BCG strain, as described in [Section 7.2](#), it is expected that approximately 100 CIS participants will be treated each in Arm A and C and 150 CIS participants in Arm B. It is expected that approximately 8 CIS participants will be treated in Arm D during the safety lead-in. [Table 10.1-1](#) summarizes the different boundaries of the exact 95% CI (based on Clopper-Pearson method) for different observed CR rates in 100 and 150 CIS treated participants. For example, if at least 40 participants with CR in a treatment group are observed among the 100 CIS treated participants (ie, CR rate  $\geq$  40%), then the lower bound of the 95% CI is above 30%.

**Table 10.1-1: Observed Complete Response Rate and Exact 95% Confidence Interval in the CIS Population**

Observed CR (CR rate [%]) (N=100)	95% Exact CI	Observed CR (CR rate [%]) (N=150)	95% Exact CI
25 (25%)	(16.9% - 34.7%)	37 (24.7%)	(18.0% - 32.4%)
30 (30%)	(21.2% - 40.0%)	45 (30.0%)	(22.8% - 38.0%)

**Table 10.1-1: Observed Complete Response Rate and Exact 95% Confidence Interval in the CIS Population**

Observed CR (CR rate [%]) (N=100)	95% Exact CI	Observed CR (CR rate [%]) (N=150)	95% Exact CI
35 (35%)	(25.7% - 45.2%)	53 (35.3%)	(27.7% - 43.6%)
40 (40%)	(30.3% - 50.3%)	60 (40.0%)	(32.1% - 48.3%)
45 (45%)	(35.0% - 55.3%)	68 (45.3%)	(37.2% - 53.7%)
50 (50%)	(39.8% - 60.2%)	75 (50.0%)	(41.7% - 58.3%)
55 (55%)	(44.7% - 65.0%)	82 (54.7%)	(46.3% - 62.8%)
60 (60%)	(49.7% - 69.7%)	90 (60%)	(51.7% - 67.9%)

An initial evaluation of efficacy and safety will be performed for each treatment group when 34 CIS participants in each treatment group have been treated and followed up to 6 months. If  $\leq 9$  (26%) participants achieve CR at 6 months, the treatment group may not be considered promising and accrual in this treatment group may then be stopped based on the recommendation of the DMC and decision of the Sponsor. If  $\geq 10$  (29%) participants achieve CR at 6 months, the treatment group will be considered promising and accrual in this treatment group could then continue to full enrollment. If the true CR rate at 6 months for a treatment group is 20%, there is a probability of 87% of observing  $\leq 9$  CR among 34 first CIS participants. If the true CR rate at 6 months for a treatment group is 40%, there is only a probability of 7% of observing  $\leq 9$  CR among 34 first CIS participants. These probabilities were considered appropriate in light of recent efficacy results of another anti-PD1 monotherapy regimen in the same indication showing an encouraging CR rate of 40.2% [95% CI: 30.6-50.4].

CIS participants will be randomized in a 1:1:1 ratio (dependent on BCG availability) after safety lead-in completion. Enrollment in the safety lead-in will be staggered so that the safety lead-in phase for Arm B is adequately assessed prior to the enrollment of Arm D. Once the number of participants for the safety lead-in is reached in Arm D, accrual will only continue in the 3 other arms. Once 34 CIS treated participants in a given treatment group have been followed for at least 6 months, an initial evaluation of efficacy and safety for that treatment group will be conducted. Accrual will not be stopped prior to this initial evaluation.

The primary analysis of the primary endpoint CR rate will be performed when all CIS treated participants with CR in each treatment group have had at least 12 months of follow up from the time of initial CR.

## 10.2 Populations for Analyses

Per Protocol Amendment 04, only safety and immunogenicity assessments will be conducted.

For purposes of analysis, the following populations are defined:

Population	Description
Enrolled Participants	All participants who sign informed consent and are registered into IRT
Treated	All randomized participants who received at least one dose of any study medication.
Immunogenicity	All treated participants with available ADA data.

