**Table 4-1: Objectives and Endpoints**

Objectives	Endpoints

 
To describe the safety and tolerability of nivolumab and nivolumab + BMS-986205, alone or in combination with intravesical BCG.
 
	
 
Incidence of adverse events (AEs), serious AEs, deaths and laboratory abnormalities in all treated participants.
 
Overall safety and tolerability will be measured by the incidence of AEs, SAEs, AEs leading to discontinuation, immune-mediated AEs, deaths, and laboratory abnormalities and changes from baseline.
 

 
To characterize the immunogenicity of nivolumab.
 
	
 
Incidence of anti-nivolumab antibodies and their potential relationship with safety.
 

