A safety lead-in will be conducted in participants randomized to receive BCG and nivolumab without or with BMS-986205 (Arms B and D, respectively) to determine safe-dose levels to be administered during the treatment phase. Enrollment in the safety lead-in will be staggered so that the safety lead-in phase for Arm B is adequately assessed prior to the enrollment of Arm D. After the safety lead-in (see [Section 5.1.1](#)), participants with CIS, with or without papillary disease, will be randomized in a 1:1:1 ratio into study Arms A through C.

Revised protocol 03 study design modifications include limiting enrollment only to participants with CIS and increasing the sample size for each arm, in order that this randomized study design will be able to demonstrate a CR rate and duration of response in CIS participants. A second key modification is that due to global shortages of BCG, only 1 BCG-containing arm (Arm B) will

move forward with randomization instead of 2 (Arms B and D). Thus, after the safety lead-in to Arm D, enrollment will be paused. Modified randomization, based on the availability of BCG at the site, allows sites facing BCG shortage at the time of participant enrollment to enroll participants in the study (Section 5.4.9). Once 150 total participants have been randomized to Arm B, the BCG-containing arm, Arm B will stop enrollment. At that point, new participants would be randomized via the “No BCG available” category to either Arm A or C, if open for enrollment (see Figure 5.1-1). Lastly, the number of non-TICE BCG treated participants was limited to 70 to ensure at least 80 participants are treated with TICE BCG in Arm B, the only strain approved in the US and many other countries.

As of 02-Jun-2021, enrollment into this study was closed. Protocol Amendment 04 removes the decision points and the efficacy follow-up along with other study procedures. As a result, randomization Phase Part 3, initial risk/benefit assessment by the Data Monitoring Committee, and Independent Pathology Review Committee (PRC) will be removed.

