### 7.1.1 Nivolumab Dosing

Participants should receive nivolumab at a dose of 480 mg as a 30-minute infusion on Day 1 of each treatment cycle (1 cycle = 4 weeks) until recurrence, progression, unacceptable toxicity, withdrawal of consent, or completion of 52 weeks of treatment, whichever occurs first. Participants randomized to Arms A or C should begin study treatment within 3 calendar days of randomization. Participants randomized to Arms B or D should begin study treatment within 3 calendar days of randomization or after 14 days from last TURBT or bladder biopsy, whichever is later.

No dose escalations or reductions are allowed for nivolumab after the safe-dose level has been determined in the safety lead-in. For Q4W dosing cycles, participants may be dosed within a  $\pm 3$  day window. Premedication is not recommended for the first dose of nivolumab.

Participants should be carefully monitored for infusion reactions during nivolumab administration. If an acute infusion reaction is noted, participants should be managed according to Section 7.7.5.

Doses of nivolumab may be interrupted (ie, infusion interruption), delayed, or discontinued depending on how well the participant tolerates the treatment. Dosing visits are not skipped, only delayed. BMS-986205 treatment should be continued if nivolumab dosing is interrupted or delayed. BMS-986205 treatment should be discontinued if nivolumab administration is discontinued.

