## **7.2 Method of Treatment Assignment**

All participants will be randomized using an Interactive Response Technology (IRT). Before the study is initiated, each user will receive log-in information and directions on how to access the IRT. After the participant's initial eligibility is established and informed consent has been obtained, the participant must be enrolled into the study by accessing an IRT to obtain the participant number. Every participant who signs the informed consent form must be assigned a participant number in IRT. The investigator or designee will register the participant for enrollment by following the enrollment procedures established by BMS. The following information is required for enrollment:

- Date that informed consent was obtained
- Year of birth
- Gender at birth

Once enrolled in IRT, enrolled participants who have met all eligibility criteria will be ready to be randomized through the IRT. Disease status data will be transferred directly from the PRC. Tumor PD-L1 expression data will be transferred directly from analyzing lab. The following information is required for participant randomization:

- Participant number
- Year of birth
- Disease status based on PRC assessment (CIS alone vs CIS with Ta vs CIS with T1)
  - CIS participants with both Ta and T1 disease will be classified as CIS with T1

- Tumor PD-L1 status (expressing [ $\geq 1\%$ ] vs non-expressing [ $< 1\%$ ] or indeterminate/not evaluable)

The randomization procedure will dynamically minimize the imbalance between treatment groups within the levels of the 2 stratification factors above (disease status and tumor PD-LI status) (see [Section 5.1.2](#)).

- Randomization will be based on the categories related to availability of BCG and BCG strains at the site at the time of participant randomization (No BCG available vs TICE BCG available vs Non-TICE BCG available)
  - For the purposes of randomization, any BCG strain that becomes approved in the US during the conduct of the study will be included in the category of TICE BCG

Study treatment will be dispensed at the study visits as listed in Schedule of Activities ([Section 2](#)). See [Section 5.1.2](#) for a description of treatment assignment during the Randomization Phase of the study.

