#### **10.3.2 Safety Analyses**

All safety analyses will be performed on the Treated Population.

Safety analyses will be performed in all treated participants and for each treatment group. Descriptive statistics of safety will be presented using National Cancer Institute (NCI) Common Terminology Criteria for Adverse Events (CTCAE) version 4.03 by treatment group. All on-study AEs, treatment-related AEs, SAEs, and treatment-related SAEs will be tabulated using worst grade per NCI CTCAE v 4.03 criteria by system organ class and preferred term. On-study lab parameters including hematology, chemistry, liver function, and renal function will be summarized using worst grade NCI CTCAE v 4.03 criteria.

Additional safety analyses will be described in the SAP finalized before database lock.

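### Does defining the Treated population as randomized and dosed leave the safety lead-in participants out of the safety analyses?

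*Combined protocol and SAP*

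**What the plan says.** Section 10.2 defines Treated as "All randomized participants who received at least one dose of any study medication" and Immunogenicity as "All treated participants with available ADA data", so the second set sits inside the first. Section 10.3.2 adds: "All safety analyses will be performed on the Treated Population". It asks for results over all treated participants and by treatment group.

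The endpoint and the sampling rule are written without the word randomized. Table 4-1 gives the endpoint as "Incidence of adverse events (AEs), serious AEs, deaths and laboratory abnormalities in all treated participants". Section 9.5.2 says: "Samples for anti-drug antibody (ADA) assessments will be collected from all participants receiving study treatment".

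Section 10.3 leaves the selection of participants for analysis to an SAP that is to be completed ahead of database lock.

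**The concern.** The protocol does not use the word randomized consistently. Section 5.1.2 describes the lead-in as enrollment into Arm B first and then into Arm D. It starts Part 1 of the randomization phase only once about 8 people have begun treatment in the Arm D lead-in, and it opens that phase to Arms A, B and C alone. Section 10.1 places the 1:1:1 allocation after the lead-in is complete. Read alone, these sections suggest that lead-in participants were enrolled but not randomized.

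If Section 10.2 used the word in that narrow sense, the lead-in would fall out of Treated and therefore out of Immunogenicity. Arm D would suffer most. Its enrollment was to pause after the lead-in, so it contains nobody else and would have no safety population. Yet the objective in Table 4-1 covers nivolumab plus BMS-986205 with BCG, which only Arm D received.

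A related worry is that Arm B mixes routes of entry. Under Section 5.1.2, a site with TICE BCG assigns only to Arm B while that arm is open, so chance plays no part there. A reader might take the by-arm tables as a comparison of randomized groups.

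**Working it through.** **Size of the group at issue.** Section 5.1.2 plans 8 participants in the Arm B lead-in and about 8 in Arm D: 8 + 8 = 16, which matches its own figure of approximately 16. It allows 8 more per arm after review by the data monitoring committee, so the ceiling is 16 + 16 = 32. The documents do not say that either extension happened.

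**What each reading gives.**

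| Sense of randomized in 10.2 | Lost from Treated | Arm D in the safety tables |
|---|---|---|
| Assigned through the response system | 0 | about 8 (up to 16) |
| Allocated in the later phase only | about 16 (up to 32) | 0 |

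Neither loss can be given as a share of the safety set, because the number treated is not stated. The 135 in Section 5.2 counts enrolled participants, and Section 10.2 defines enrolled as consented and registered.

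**Which sense governs.** The relevant sections are:

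- Section 7.2, on treatment assignment: "All participants will be randomized using an Interactive Response Technology (IRT"). It makes no exception for the lead-in.
- Section 9, Treatment Phase: the phase begins with the randomization request to the response system. Under the protocol, no first dose comes before that step.
- Section 5.1: "A safety lead-in will be conducted in participants randomized to receive BCG and nivolumab without or with BMS-986205 (Arms B and D, respectively"). The Synopsis says the same.
- Section 7.1.1: "Participants randomized to Arms B or D should begin study treatment within 3 calendar days of randomization", or later if a recent resection or biopsy requires it. Arm D has only lead-in participants, so this rule would apply to nobody in Arm D if they were not randomized.
- Table 2-3, the on-treatment schedule for Arms B and D, has a randomization entry at Cycle 1 Day 1.
- Section 5.1.1: once a safe dose is established, the arm is opened to randomization again, which implies that it had been open to randomization before.

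Against these stand Sections 5.1.2 and 10.1. They say when the multi-arm scheme starts and in what ratio. Neither defines an analysis population, and neither says that lead-in participants are not randomized.

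**Check against intent.** Section 10.1 expects about 8 participants to be treated in Arm D, Table 4-1 includes the Arm D combination, and Section 10.3.2 wants safety for each treatment group. The narrow reading defeats all three and the inclusive reading satisfies them. With every participant passing through Section 7.2, the treated participants of Table 4-1 and the randomized and dosed participants of Section 10.2 are the same people.

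**The case for a change.** The strongest case for a change is that one word controls every remaining analysis. Section 5.1 itself uses the word both ways: it calls lead-in participants randomized, then says that participants will be randomized to Arms A through C after the lead-in. The Treated definition carries a condition that the endpoint and the sampling rule lack. Naming the lead-in would take a few words, and the SAP was still to be written. It is true that the usage is loose and that such a clause would do no harm. But the clause would restate Section 7.2 and leave the analysis sets as they are.

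The Arm B point is weaker. Participants from TICE sites are assigned within the randomization scheme of Section 5.1.2, so they belong to Treated on either reading. The planned share with fixed assignment, at least 80/150 = 53.3%, uses targets that Section 10.1 labels as the original design. The trial closed far short of them, with 135 enrolled over all arms by early April 2021. Assignment by BCG availability came only with Revised Protocol 03 (01-Nov-2019), and the sponsor could switch TICE sites to 1:1:1. The figure therefore describes no group that was actually enrolled. Sections 5.4.5 and 5.4.9 rule out formal comparison between arms, and Section 5.1.2 calls randomization administrative and for balance. A marker for route of entry in descriptive adverse-event tables is a reporting preference.

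Arm D can show little about uncommon events. With none seen, the exact two-sided 95% upper limit is 1 − 0.025^(1/8) = 36.9% for 8 participants and 1 − 0.025^(1/16) = 20.6% for 16. These limits reflect the size of the arm and hold on the inclusive reading as well. They do not measure a fault in the definition.

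**Conclusion.** The concern does not call for a change. Read with Sections 7.2 and 9, the definition already takes in every dosed lead-in participant: 0 are lost from Treated, and none leave Immunogenicity through this wording. The loss of about 16 (at most 32) arises only on a reading that conflicts with the assignment section, the dosing rules, the schedule for Arms B and D, and the safety objective. What remains is a clerical looseness in Sections 5.1.2 and 10.1.

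Two assumptions support this. Lead-in participants were entered through the response system as Section 7.2 requires; someone dosed outside it would be a protocol deviation, and the SAP's rules on participant selection would have to deal with that. The counts are planned lead-in sizes, since the documents give no numbers treated by arm.

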**Table 2-4: Follow-up Procedural Outline (CA2099UT)**

Procedure	Follow-up a Visits 1 and 2	Notes b
Safety Assessments		
Targeted Physical Examination, Measurements, Vital Signs, and Performance Status	See note	Weight, blood pressure, heart rate, temperature and ECOG Performance Status, to be performed only as clinically indicated.
Adverse Events Assessment (including Serious Adverse Events)	See note	Record at each visit. SAEs should be approved in RAVE within 5 days from entry. All AEs and SAEs must be collected for a minimum of 100 days following the last dose of study treatment. Participants will be followed for all SAEs, non-serious AEs of special interest (as defined in Section 9.2.9 ), and all AEs and SAEs associated with confirmed or suspected SARS-CoV-2 infection until resolution, the condition stabilizes, the event is otherwise explained, the event is deemed irreversible, the participant is lost to follow-up (as defined in Section 8.3 ), or for suspected cases, until SARS-CoV-2 infection is ruled out. See Section 9.2 for additional information on collection of AEs and SAEs.
Concomitant Medication Assessment	X	Record at each visit.
Subsequent Bladder Cancer Treatment	X	
Laboratory Tests		
CBC with Differential, Chemistry Panel, Thyroid Testing	Visit 1-yes Visit 2 - only if toxicities are present	For full list of assessments, see Section 9.4.1 .
Pregnancy (WOCBP only)	X	Serum or urine pregnancy testing.
Blood Samples for Immunogenicity for Nivolumab	See notes	Refer to Table 9.5.2-1 .

a Participants must be followed for at least 100 days after last dose of study treatment. Follow-up visit #1 should occur 30 days from the last dose ( $\pm 7$  days) or can be performed on the date of discontinuation if that date is greater than 30 days from the last dose. Follow-up visit #2 occurs approximately 100 days ( $\pm 7$  days) from last dose of study treatment. Both follow-up visits should be conducted in person.

- b Some of the assessments referred to in this section may not be captured as data in the eCRF. They are intended to be used as safety monitoring by the treating physician. Additional testing or assessments may be performed as clinically necessary or where required by institutional or local regulations.

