### **10.3 Statistical Analyses**

The statistical analysis plan (SAP) will be developed and finalized before database lock and will describe the selection of participants to be included in the analyses, and procedures for accounting for missing, unused, and spurious data.

A description of the participant population will be included in the statistical output and reported, including subgroup of age, gender, and race.

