#### **10.3.3 Other Analyses**

Immunogenicity analyses will be described in the SAP finalized before database lock.

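### Does the broad Immunogenicity population in Section 10.2 leave anti-nivolumab antibody incidence without a usable denominator?

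*Combined protocol and SAP*

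**What the plan says.** After Amendment 04 only safety and immunogenicity are analyzed. Table 4-1 gives the immunogenicity endpoint as "Incidence of anti-nivolumab antibodies and their potential relationship with safety".

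Section 10.2 builds the analysis set in two steps. The Treated population is "All randomized participants who received at least one dose of any study medication". The Immunogenicity population is "All treated participants with available ADA data".

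Section 9.10 says how results are reported. It lists several kinds of positive status, and the sentence ends "or baseline positive) and ADA negative status, relative to baseline".

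Table 9.5.2-1 schedules one pre-treatment sample (predose, Cycle 1 Day 1), then Day 1 of Cycles 3, 6 and 10, and the two follow-up visits. Its footnote on early stopping reads "If a participant permanently discontinues study drug treatment during the sampling period, then they will move to sampling at follow-up visits". Table 2-4 adds "Both follow-up visits should be conducted in person".

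Section 10.3 says that the SAP "will describe the selection of participants to be included in the analyses" and that it will cover missing data. Section 10.3.3 says only "Immunogenicity analyses will be described in the SAP finalized before database lock". That SAP text is not in the documents available for review.

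**The concern.** Incidence is a proportion, so it needs a stated denominator. To judge a post-baseline ADA result against baseline, a participant needs a baseline result and at least one later result. Section 10.2 asks for neither. On a literal reading it admits two groups that cannot be classified:

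- participants with a baseline sample only, who sit in the denominator but can never show a post-baseline positive and so dilute the rate;
- participants with no baseline result, whose positives might be counted as new and so raise it.

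A related question concerns the numerator. Section 9.10 treats baseline positive as a kind of positive status, and Table 4-1 does not say whether such participants count towards incidence.

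Immunogenicity is one of the two objectives left in the trial. If the Section 10.2 set were used unchanged as the denominator, a reader could not tell which of these effects was in the published figure, and the same set might carry into any summary of safety by ADA status.

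**Working it through.** The documents state no ADA rate, ADA sample size or missing-sample rate, so there is no figure of the plan's own to reproduce. The check compares the texts and then sizes the effect on assumed inputs.

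**Texts side by side**

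- *Is the Section 10.2 set named as the denominator?* No. Section 10.3.2 ties all safety analyses to the Treated population. No sentence ties ADA incidence to the Immunogenicity population; Section 10.3.3 defers the matter.
- *Does a broad set have a use?* Yes. Baseline positive is a reported status in Section 9.10 and needs only the Cycle 1 Day 1 sample. Narrowing Section 10.2 to people with both samples would drop baseline-only participants from a summary of baseline prevalence.
- *Does Section 10.2 lead to counting a positive without a baseline as new?* No. Section 9.10 requires status relative to baseline. A participant with no baseline result cannot be classified on those terms, so calling the positive new would depart from Section 9.10.
- *How easily does someone become baseline-only?* A participant still on treatment at Cycle 3 has a scheduled sample then. One who stops earlier moves to follow-up sampling at about 30 and 100 days after the last dose. Both of those samples must be missing.

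**Size of the effect**

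All inputs are assumed: true post-baseline incidence p = 0.10, baseline-only share f, missing-baseline share m, baseline prevalence b.

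1. Baseline-only participants in the denominator, p(1 − f):
   - f = 0.02: 0.10 × 0.98 = 9.8%
   - f = 0.05: 0.10 × 0.95 = 9.5%
   - f = 0.10: 0.10 × 0.90 = 9.0%
2. Missing-baseline positives all counted as new, p(1 − m) + m[p + b(1 − p)], with b = 0.05, so the bracket is 0.10 + 0.045 = 0.145:
   - m = 0.02: 0.098 + 0.0029 = 10.1%
   - m = 0.05: 0.095 + 0.00725 = 10.2%
3. Both, f = m = 0.05: 0.10 × 0.90 + 0.05 × 0.145 = 9.7%.
4. Baseline positives put in the numerator, (1 − f)[p + b(1 − p)] + f·b:
   - f = 0.05, b = 0.02: 0.95 × 0.118 + 0.001 = 11.3%
   - f = 0.05, b = 0.05: 0.95 × 0.145 + 0.0025 = 14.0%
   - f = 0: 11.8% and 14.5% respectively

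Item 4 gives the largest figures, but they come from the numerator. With no baseline-only participants at all, the effect is slightly larger. A narrower population in Section 10.2 would not cure it.

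**Against sampling error**

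For scale, take N = 135, the number enrolled as of early April 2021 (Section 5.2). The numbers treated and with ADA data are not given and may differ. Then f of 2% to 10% is 135 × 0.02 = 2.7 to 135 × 0.10 = 13.5, or about 3 to 14 people. With 5% lacking a needed sample, 13/128 = 10.2% becomes 13/135 = 9.6%, with an exact 95% interval of 5.2% to 15.9%. As a stress case with 20% lacking one, 11/108 = 10.2% (5.2% to 17.5%) becomes 11/135 = 8.1% (4.1% to 14.1%), still heavily overlapping. At 30% lacking one and incidence near 20%, 19/94 = 20.2% becomes 19/135 = 14.1%. That would be visible, but nothing in the sampling schedule points to losses of that order.

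**The case for a change.** The best case for a change is that Section 10.2 is not silent. It states a rule, the rule is broader than the reporting convention in Section 9.10 needs, and an SAP author who copied it would inherit the gap. The SAP cannot be inspected here, so its contents cannot be assumed. The endpoint is one of only two that remain. Two analysts working from this text could report different rates from the same data, especially over baseline positives. One added line would settle it, with no new data collection.

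Part of this stands. No section available for review states which subset is the denominator for incidence relative to baseline, or whether a baseline positive counts as incident.

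The rest is conditional. The harm arises only if the SAP reuses the broad set as the denominator, and nothing shows that it does. Choosing who enters each analysis and handling missing samples are the tasks that Section 10.3 assigns to the SAP. A broad population with evaluable subsets below it is a legitimate structure. That the endpoint means post-baseline incidence is an inference from Section 9.10, since Table 4-1 says only incidence; the inference is natural, but Section 10.2 cannot be faulted for failing a definition that the protocol does not state.

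**Conclusion.** No change to the plan is needed. This is detail left to the SAP, which the protocol requires to be finalized before database lock and which it charges with participant selection, missing data and the immunogenicity analyses. An analyst would ordinarily compute post-baseline incidence among participants with a baseline and at least one later result, show baseline positives under their own heading, as the categories in Section 9.10 already allow, and keep the broader set for baseline prevalence. None of that conflicts with Section 10.2.

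The denominator effect is 0.2 to 1.0 percentage points at an assumed incidence of 10% and a baseline-only share of 2% to 10%, well inside sampling error at about 135 participants. The missing-baseline effect is 0.1 to 0.2 points and needs a classification that Section 9.10 does not support. The larger figures of 11.3% and 14.0% concern how baseline positives are counted, which is a separate matter from the population definition.

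The conclusion rests on assumed rates and on most treated participants giving at least one post-baseline sample, which the move to in-person follow-up sampling makes likely. The analysis is descriptive, no hypothesis or decision rule uses ADA status, and its relation to safety is exploratory.
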